### 2.3.2 Risk Assessment

#### 2.3.2.1 Hypotension and Bradycardia:

Studies have shown that the peak effect of oral propranolol on blood pressure and heart rate occurs 1 to 3 hours after it is taken[28, 29]. As such, current recommendations are that patients should have HR and BP done at baseline and also hourly for the first 2 hours after a dose increase, and at least once after the target dose is achieved. As dose response is generally most significant after the first dose, once normal vitals are obtained with the first dose there is no recommendation that vitals should be re-checked at the same dose level, unless the patient is very young, has cardiovascular issues or co-morbidities, or if clinical complaints arise.

Pediatric patients must have vitals within the normal range for their age group, and adults with normal established vitals, prior to starting a dose. Dose escalations will take

place as given in the table above. Patient must have no evidence of clinical contraindications with acceptable HR and BP parameters prior to dose escalation occurring. If individuals are found to have a fall in their blood pressure or heart rate outside of normal range, they will have dose de-escalation to the prior tolerated dose level. If they are able to tolerate this lower dose level with normal parameters and no clinical symptomatology they will have a re-challenge of the dose escalation after 2 weeks. If on re-escalation they once again have fall in HR and blood pressure, they will again undergo dose de-escalation to the prior tolerated dose level for 2 weeks and re-evaluated again until the end of the 8-week study. If the patients are already at the lowest doses, they will be given a 2-week rest and re-evaluated after 2 weeks. If HR and BP then fall within normal parameters they will be reintroduced to the study at the lowest study dose of propranolol. If patient is once again found to have fall in HR/BP below normal parameters for age upon an attempt to re-start propranolol, they will be removed from the study. That is, all patients who do not tolerate a dose increase for the 2nd time will be held at the last tolerated dose until the end of the study. If a patient cannot tolerate the lowest doses twice, they will be removed from the study.

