At the 2nd-week re-evaluation, they will be escalated to the new dose (1mg/kg/day) if the baselines HR and BP are WNL. Patients will have HR and BP noted after first new dose (1mg/kg/day) of propranolol to ensure that the propranolol is tolerated. If the HR and BP are WNL, they will continue on this new dose and re-evaluated in 2 weeks for the 4th-week evaluation. If they have a drop in HR and BP to below normal range, they will be de-escalated and remain on the prior dose (0.5mg/kg/day) until the next visit (week 4).

At the 4th and 6th-week evaluation, their baseline vitals will be evaluated and their propranolol escalated to the next dose (if vitals are WNL) and have their HR and BP assessed after first new dose. Propranolol will stay increased or held at old dose depending on HR and BP after the first new dose as described above. If on re-evaluation in 2 weeks a patient continues to have below normal HR and blood pressure on re-challenge of the escalated dose, they will not be escalated and remain at the last tolerated dose for the remainder of the 8 week period with no further re-challenges. For patients with below normal HR and BP and needed their doses held, they will be reported as AEs.

At each study visit, patients will be asked to complete validated questionnaire to assess for tolerance to propranolol treatment, subjective changes in lymphedema symptoms, and self-reported function and activities of daily living (SF-36, LYMPH—ICF, and LYMPH—ICF—LL) (See attached documents, Appendix 2). Physical examination will include weight and BMI, vitals (HR, BP), and measurement of girth of normal and affected extremity.

MRIs and blood tests will be performed at study entry and study endpoint to assess for changes in lymphedema tissue composition[21-23] in response to propranolol.

Blood draws will be performed at study entry, at the midpoint, and study endpoint to assess for changes in circulating biomarkers in response to propranolol treatment.

Correlative biomarkers assessed will include markers of progenitor, endothelial, lymphatic, macrophage, and adipocyte cells, and expression of beta-adrenergic receptors (Table 3).

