## **5.0 TREATMENT PROGRAM**

### **5.1 Overview of Treatment Plan**

Patients will be provided with propranolol prescriptions. Dosing is weight-based (corrected to the closest 10kg increment) and will be prescribed by the PI after medical evaluation by the study cardiologist.

The starting dose of propranolol will be 0.5 mg/kg/day, which is the current institutional dose for initial treatment for cardiovascular and hemangioma indications in children. Dose escalation to 1 mg/kg/day will take place at the 2-week evaluation in the absence of clinical contraindications. If patient tolerates 1 mg/kg/day dose, they will be escalated to 2 mg/kg/day at the 4-week evaluation. In the absence of clinical contraindications, dose escalation will be increased to 3mg/kg/day at week 6 and continued for the duration of the study. A maximum of 8-weeks of therapy may be administered.

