#### **5.2.2 Intra-Patient Escalation**

The starting dose will be 1 mg/kg/day (BID) with dose escalation up to 3 mg/kg/day (BID) in the absence of clinical contra-indications. There will be no escalations beyond 3 mg/kg/day (Table 1).

At the return visit, patients must have no evidence of clinical contraindications with normal HR and BP parameters prior to dose escalation occurring. They will be re-evaluated 2 hours after the first escalated dose. If individuals have normal heart rate and blood pressure and report no clinical symptoms (dizziness, increased fatigue), they will be given the new escalated dose and re-evaluated 2 hours after the new dose. If their HR and BP are within normal limits (WNL), they will be sent home on this new escalated dose and will return in another 2 weeks for evaluation. If individuals are found to have a fall in their blood pressure or heart rate below the normal value at 2 hours after the new dose, they will not be escalated and will be sent home at the current dose. They will return in 2 weeks for evaluation for dose escalation.

If individuals are found to have a fall in their blood pressure or heart rate below the normal value at the return visit *and* clinically asymptomatic, they will be held at the current tolerated dose level (no escalation). If they are able to tolerate this lower dose level with normal parameters and no clinical symptomatology they will return for evaluation of dose escalation at the next visit. If their parameters are WNL, they will be escalated and evaluated. If they do not tolerate dose escalation, they will be held at the current tolerated dose of propranolol until the end of the study without further attempts to escalate. Patients who are not able to tolerate dose escalation at 2 consecutive visits will have no more dose escalation challenges and stay for the remainder of the study at the current tolerated dose.

Individuals found to have a fall in HR and BP below normal parameters at initiation (0.5mg/kg/day, week 1) will be removed from the study for 1 week. At week 2 they will be re-evaluated. If HR and BP are within normal parameters they will be reintroduced to the study. If patient is once again found to have fall in HR/BP below normal parameters upon an attempt to re-initiate (failed the lowest initiation dose of 0.5mg/kg/day twice), they will be removed from the study.

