## 6.0 DOSE MODIFICATIONS FOR ADVERSE EVENTS

**The Study Chair must be notified of any dosage modification.**

### 6.1 Dose Modifications for Potential Propranolol Specific Side Effects

#### 6.1.1 Hypotension and Bradycardia

**Baseline blood pressure (BP)** is defined as the blood pressure obtained at the examination used for study enrollment. This baseline BP should be obtained as follows: 1) Obtain 3 serial blood pressures from the same extremity with the patient in the same position that are separated by at least 5 minutes. Avoid using the lower extremity if possible. BP will not be obtained from the affected limb. 2) Average the systolic blood pressure from the 2nd and 3rd measurements. 3) Average the diastolic blood pressure from the 2nd and 3rd measurements. 4) The baseline BP is the average of the systolic over the average of the diastolic measurements.

Heart rate will be measured by palpation of the radial pulse serially from the same extremity for 15 secs, separated by at least 5 minutes. In the case of extremity LMs, pulse rate will not be obtained from the affected limb. 2) Average the pulse rate from 2nd and 3rd measurements.

6.1.1.1 Patient must have no evidence of clinical contraindications with normal HR and BP parameters prior to dose escalation occurring. If individuals are found to have a fall in their blood pressure or heart rate to below normal limits, but asymptomatic:

- a. patient will be not have dose escalation
- b. patient will be evaluated for dose escalation at the next 2-week cycle.
- c. if HR and BP fall below normal ranges and patient is symptomatic, propranolol will be held for 2 weeks, and re-introduced at the next visit at the lowest tolerated dose.
- d. if patient is at the lowest dose already (0.5mg/kg/day), they will be pulled from the study and re-evaluated at the next visit.
- e. Patients receiving 0.5mg/kg/day who experience HR or BP decrease below the normal range at 4 weeks must be taken off protocol therapy.

Table 5. Side effects and propranolol dosing guidelines

Hypotension and Bradycardia	Propanolol Dosing Guidelines
Within normative range	No change in dose
Below normal range, asymptomatic	Cardiology evaluation, EKG, echocardiogram; if cardiac status is acceptable, patient will not have dose escalation and remain at current dose level with subsequent re-evaluation at 2 weeks

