**14.2.3 Stop or change rules**

Patients will be removed from study if they cannot tolerate the initiation dose of propranolol. Patients who failed 2 challenges to escalate to 1mg/kg/day (lowest study dose) will be pulled from the study. Patients who failed 2 challenges to escalate to subsequent doses will be kept at the highest tolerated dose without any further attempts to escalate through the study.

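### The propranolol titration and removal rules conflict on four points, and no section is named as governing

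*Combined protocol and SAP*

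**What the plan says.** Titration and removal rules stand in Table 1 (two copies), 2.3.2.1, 2.4, 5.1, 5.2.2, 6.1.1.1 with Table 5, and 14.2.3.

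- **Starting dose.** Section 5.1: "The starting dose of propranolol will be 0.5 mg/kg/day". Table 1, 2.4 and the last paragraph of 5.2.2 agree. Section 5.2.2 nevertheless opens: "The starting dose will be 1 mg/kg/day (BID) with dose escalation up to 3 mg/kg/day (BID").
- **Which dose is lowest.** Section 14.2.3 gives that label to 1 mg/kg/day. Section 6.1.1.1d gives it to 0.5: "if patient is at the lowest dose already (0.5mg/kg/day), they will be pulled from the study and re-evaluated at the next visit".
- **Two failed escalations to 1 mg/kg/day.** Section 14.2.3: "Patients who failed 2 challenges to escalate to 1mg/kg/day (lowest study dose) will be pulled from the study". Section 5.2.2: "Patients who are not able to tolerate dose escalation at 2 consecutive visits will have no more dose escalation challenges and stay" at the dose they tolerate. Section 2.3.2.1, speaking of all patients who fail an increase a second time, says they "will be held at the last tolerated dose until the end of the study". Section 2.4: "they will not be escalated and remain at the last tolerated dose for the remainder of the 8 week period with no further re-challenges".
- **Failed first dose.** Section 5.2.2 takes the patient off for 1 week and looks again at week 2. Sections 2.3.2.1 and 2.4 give a 2-week rest.
- **Symptomatic fall in heart rate or blood pressure after a new dose.** Sections 5.2.2 and 2.4 keep the patient on the prior dose and set no symptom condition. Section 6.1.1.1c and Table 5 stop the drug for 2 weeks. Restart is at the lowest tolerated dose in 6.1.1.1c and at the prior tolerated dose in Table 5.
- **Precedence.** Section 10.1 refers to Section 6.0 for adverse events that require removal. No section says which text governs when two differ.

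**The concern.** Section 11.2.2 makes tolerability of escalating doses the primary endpoint. Section 8.4 reports toxicity at each dose and evaluates response at the highest tolerable dose. The titration rules therefore define the treatment being studied. Where two sections give different instructions for the same event, obeying one breaks the other.

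At stake are the first dose given, who stays on treatment, how long a patient rests after a failed first dose, and whether a symptomatic patient, who may be as young as 12, keeps taking the drug. The last of these is the most important for safety.

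**Working it through.** The plan gives no figure on this point, so there is nothing to reproduce. The check compares the sections and traces one patient through the visits in 14.2.2 (weeks 1, 2, 4, 6 and 8). Exposure is days × mg/kg/day, ignoring single test doses.

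**1. Starting dose.** The ratio is 1 / 0.5 = 2. Only the first sentence of 5.2.2 gives 1 mg/kg/day as the start. Section 14.2.3 itself treats the initiation dose as separate from, and below, 1 mg/kg/day, so its lowest-dose label does not fit its own rule.

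**2. Two failed escalations to 1 mg/kg/day (weeks 2 and 4).**
- 14.2.3: treatment ends about week 4.
- 2.3.2.1, 2.4 and 5.2.2: 0.5 mg/kg/day continues from week 4 to week 8, which is 28 × 0.5 = 14 mg/kg more.

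These are opposite dispositions for one event. Section 14.2.3 applies its own keep-at-tolerated-dose rule only to later doses, so removal at 1 mg/kg/day does not read as loose wording. With the planned 15–20 patients, one such patient is 1/20 = 5.0% to 1/15 = 6.7% of those enrolled.

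**3. Failed first dose, every later step tolerated, one step per visit (illustration).** The week numbering is not fixed. Sections 2.4 and 5.2.2 imply that week 2 falls 7 days after initiation, while 5.1 calls the visit a 2-week evaluation.
- 7-day numbering, 1-week rest, restart at week 2: 14×0.5 + 14×1 + 14×2 = 49 mg/kg, reaching 2 mg/kg/day.
- 7-day numbering, 2-week rest: it ends at week 3, when no visit is scheduled. Restart at the week-4 visit gives 14×0.5 + 14×1 = 21 mg/kg, reaching 1 mg/kg/day. An unscheduled week-3 restart gives 7×0.5 + 14×1 + 14×2 = 45.5 mg/kg, reaching 2 mg/kg/day.
- 14-day numbering: both rules restart at the week-2 visit and give 49 mg/kg.

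The difference runs from 49 − 49 = 0 to 49 − 21 = 28 mg/kg.

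**4. Symptomatic fall after the first 2 mg/kg/day dose at week 4; exposure in weeks 4–8.**
- 5.2.2 and 2.4: 14×1 + 14×2 = 42 mg/kg if the week-6 re-challenge is tolerated, or 14×1 + 14×1 = 28 if it is not.
- Table 5: 14×0 + 14×1 = 14 mg/kg.
- 6.1.1.1c, taking the lowest tolerated dose literally as 0.5: 14×0 + 14×0.5 = 7 mg/kg.

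**The case against.** The strongest reply is that most of this is untidy drafting that a small single-institution trial would resolve in practice.

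- **Starting dose.** The opening paragraph of 5.2.2 cites Table 1, which says 0.5. The principal investigator prescribes after cardiology evaluation (5.1). The Abstract reports no significant haemodynamic effects at 0.7–1 mg/kg/day. This stands: the sentence is probably leftover text, and a doubled first dose is unlikely. It still sits in the operative escalation section.
- **Symptomatic falls.** Section 6 addresses them expressly, the Table 1 footnote allows holding, and 2.4 mentions held doses. A careful reader would probably follow Section 6. But 5.2.2 adds an asymptomatic condition for falls found at a return visit and omits it for falls after a new dose. The reference in 10.1 covers adverse-event removals only, and Section 6 disagrees with itself on the restart dose.
- **Removal at 1 mg/kg/day may be intended.** The Abstract reports rebound worsening below 0.7 mg/kg/day, a plausible reason for a separate rule. This stands as a reason to let the investigators choose. It does not reconcile 14.2.3 with three other sections.
- **The endpoint is barely touched.** A patient who twice fails 1 mg/kg/day has 0.5 as the highest tolerated dose under either rule. Every treated patient is evaluable for adverse events (12.1), and every eligible treated patient is in the main response analysis (11.5). This stands and limits the claim to dosing, safety handling and retention on treatment.

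Two stronger readings are tempting. One takes 6.1.1.1e, "Patients receiving 0.5mg/kg/day who experience HR or BP decrease below the normal range at 4 weeks must be taken off protocol therapy", as a second removal rule for failed escalation. Its natural meaning is intolerance of 0.5 itself. The other takes Table 5, or the first sentence of 14.2.3, as removal after a single failure at 0.5. The Table 5 clause follows an instruction to re-evaluate after 2 weeks, 6.1.1.1d also provides for re-evaluation, and 14.2.3 can be a short form of failing twice.

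**Conclusion.** The four conflicts are real and stand in the current text. The clearest is the disposition after two failed escalations to 1 mg/kg/day; the one that matters most for safety is the handling of a symptomatic fall. Oversight by the investigator and cardiologist makes divergent dosing less likely but does not say which rule applies.

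For one patient, the size is 4 weeks and 14 mg/kg of treatment in conflict 2, 0 to 28 mg/kg in conflict 3, and 7 to 42 mg/kg across the competing rules in conflict 4. Conflict 3 depends on the week numbering and on when the patient restarts. Conflict 4 depends on a literal reading of the lowest tolerated dose.

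A reader might try to infer a frequency from Table 7. Its rates of asymptomatic hypotension (2.8%) and bradycardia (0.9%) give a chance of at least one such fall between 1 − (1 − 0.028)^15 = 34.7% and 1 − (1 − 0.037)^20 = 53.0%, where 3.7% assumes no overlap. These are infant rates for asymptomatic falls, with no dose attached. They do not give the frequency of any of the four conflicts, and the documents offer no other basis for one. Nor do the documents support a claim that adverse events would be missed or patients lost from the analysis set.

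**What to change.** One amendment to the text:

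1. Change the first sentence of 5.2.2 to 0.5 mg/kg/day and delete the label in 14.2.3 that makes 1 mg/kg/day the lowest dose.
2. State one disposition for two failed escalations to 1 mg/kg/day in all sections. Either the patient stays at 0.5, as three sections say, or the 14.2.3 exception is written into 2.3.2.1, 2.4 and 5.2.2. Leave 6.1.1.1e as the stop for a fall on 0.5 itself.
3. Set one rest period after a failed first dose that ends at a scheduled visit, with one re-challenge before removal. This requires saying whether week 2 is 7 or 14 days after initiation.
4. State in 5.2.2 and 2.4 that any symptomatic fall means a hold under Section 6, with restart at the prior tolerated dose.
5. Put these rules in one table and have every section cite it.

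The choices in items 2 and 3 are clinical and belong to the investigator and study cardiologist. The cost is the amendment itself: no added patients, and no added visits if the rest ends at a scheduled visit.

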**14.2.4 Plans for interim analyses and/or futility analyses**

This study only lasts 8 weeks and no interim analyses nor futility analyses are planned.

**14.2.5 Information to be monitored**

- a. Information to be monitored include assessment of data quality, timeliness and patient recruitment and retention, accrual and retention consistent with plans for diversity and generalizability.
- b. A review of outcome and adverse event data to determine whether there is any change to the risk/benefit ratio of the study, if a stop rule has been invoked, or a study endpoint has been reached whether the study should continue as originally designed, be changed, or be stopped.
- c. An assessment of external factors or relevant information (eg. developments in the literature, results of related studies, etc) that may have an impact on the safety of participants or on the ethics of the

research study.

#### 14.2.6 Communication

The PI will be available to the study coordinator, study patients, and the DSMB by person, phone, or email (study coordinator and DSMB) for any concerns. Since this is an IND exempt study, the only communication with the FDA is for adverse event reporting (Postmarketing 15-day “Alert Report”)

